6.4. Covariates and Subgroups

As a protocol defined exploratory analysis, HAI antibody response following the second vaccination will be summarized stratified by the following covariates: age (categorical: 19-34, 35-49, 50-64, 65-80, \geq 80), sex (male, female), body mass index (\leq 30, \geq 30), and prior

receipt of seasonal influenza vaccine(s) (neither 2016-2017 nor 2017-2018, 2016-2017 only, 2017-2018 only, both 2016-2017 and 2017-2018, unknown), and these covariates will be considered in statistical modeling as described in Section 8.3. As these analyses are exploratory the study was not powered for any subgroup analyses.

6.5. Missing Data

All attempts will be made to collect all data per protocol. As missing data are expected to be minimal, no imputation will be performed for missing values. Any data point that appears to be erroneous or inexplicable based on clinical judgment will be investigated as a possible outlier. If data points are identified as outliers, sensitivity analyses will be performed to examine the impact of including or excluding the outliers. Any substantive differences in these analyses will be reported.

6.6. Interim Analyses and Data Monitoring

Interim analyses will only be used to terminate this trial in the event that unanticipated safety events deemed to be of sufficient concern require such action by the sponsor. These assessments will not be made on the basis of testing a formal statistical hypothesis; therefore, p-value adjustment will not be made to any analyses. A DSMB will be convened by DMID to review study progress and participant, clinical, safety, and reactogenicity and immunogenicity data.

An interim analysis of immunogenicity is planned, as described in section 6.2 which includes a series of Expedited Interim Immunogenicity Reports of serum HAI and Neut antibody responses. This information will be reviewed due to the extraordinary need to inform public health decision makers in their preparations for their response to a potential 2017 A/H7N9 pandemic. Although interim immunogenicity results will not be used to make decisions concerning the conduct of this trial, they may be used to make decisions on activities external to this trial, e.g., designing future trials of the 2017 H7N9 IIV with and without AS03 adjuvant in other age groups.

Additionally, a preliminary report of safety and immunogenicity data through Day 43 will be prepared as described in section protocol section 11.6; though this report will be released while subjects remain in the trial for long-term safety and immunogenicity follow-up, it will be considered the final analysis of these data.

Emergent public health needs may dictate additional interim safety, reactogenicity, and/or immunogenicity analyses be performed on available information at any time during the trial. If this occurs, immunogenicity data will be analyzed as results are available from the central immunogenicity laboratory.

6.6.1. Interim Safety Review

An interim safety review may include enrollment and demographic information, medical history, concomitant medications, physical assessments, clinical laboratory values, dosing compliance, and solicited and unsolicited AE/SAEs. Additional data may be requested by the DSMB, and interim statistical reports may be generated as deemed necessary and appropriate by DMID. The DSMB may receive data in aggregate and presented by treatment arm. The

DSMB may also be provided with expected and observed rates of the expected AEs in an unblinded fashion, and may request the treatment assignment be unblinded for an individual subject if required for safety assessment. The DSMB will review grouped and unblinded data in the closed session only. The DSMB will meet and review this data at scheduled time points or ad hoc as needed during this trial as defined in the DSMB charter. As an outcome of each review/meeting, the DSMB will make a recommendation as to the advisability of proceeding with study vaccinations (as applicable), and to continue, modify, or terminate this trial. Summaries prepared for the DSMB are defined separately in a report shell reviewed and approved by the DSMB.

Additionally, this trial will be monitored to determine if any of the halting rules described in Protocol Section 9.5 are met.

6.6.2. Interim Immunogenicity Review

There is no plan to halt this trial prior to full enrollment and completion of all follow-up visits based on interim immunogenicity results. A series of Expedited Interim Immunogenicity Reports of HAI and Neut serum antibody responses will be generated as described in Section 6.2.

Immune responses will be summarized in terms of strain-specific 2017 A/H7N9 HAI and Neut antibody titers and the relationship to study vaccine dosage and adjuvant use. It is anticipated that all analyses will be carried out in parallel for both assays, but reports may be prepared separately for HAI and Neuts if results are available on different timelines. Interim analyses will focus on rates of titers ≥1:40, seroconversion (defined as either a prevaccination titer <1:10 and a post-vaccination titer ≥1:40 or a pre-vaccination titer ≥1:10 and a minimum four-fold rise in post-vaccination titer) GMTs, along with corresponding 95% confidence intervals. No formal hypothesis testing will be included in the interim analysis. All interim analyses will use the mITT population.

Tables and figures to be included in in the Expedited Interim Immunogenicity Reports are indicated with the symbol † in the title. These include Table 29 and Table 31 presenting summaries and 95% CIs of HAI and Neut antibodies respectively by treatment arm, Table 33 and Table 35 presenting summaries and 95% CIs of HAI and Neut antibodies respectively by treatment arm and age stratum.

6.7. Multicenter Studies

Although randomization was stratified by site, data will be pooled across all clinical sites for all analyses. Center effects are not anticipated because the sites are using standardized procedures for vaccination and assessment of solicited and unsolicited AEs, and the study relies on a central laboratory for immunogenicity assessments.

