approximately 240 (up to 300) individuals greater than or equal to

(≥) 65 years old who have no history of influenza A/H7N9

infection or prior receipt of an influenza virus H7 subtype vaccine.

Number of Sites: Up to 9 Vaccine and Treatment Evaluation Unit (VTEU) sites

Study Duration: Approximately sixteen (16) months

Subject Participation

Duration:

Approximately thirteen (13) months

Estimated Time to Complete

Enrollment:

Approximately 12 weeks

Description of Agent:

Two doses delivered intramuscularly (IM) approximately 21 days apart of a monovalent inactivated pre-pandemic influenza A/H7N9 vaccine (2017 H7N9 IIV) manufactured by Sanofi Pasteur, at different dosages administered with AS03 adjuvant

(GlaxoSmithKline Biologicals (GSK)) and Phosphate Buffered Saline (PBS) diluent (3.75 micrograms/0.5mL of hemagglutinin (HA) from A/Hong Kong/125/2017 H7N9 vaccine per dose), or at dosages administered with AS03 adjuvant (GlaxoSmithKline Biologicals (GSK)) (7.5 and 15 micrograms /0.5mL of

hemagglutinin (HA) from A/Hong Kong/125/2017 H7N9 vaccine per dose) or without adjuvant (15 mcg HA and 45 mcg HA per

dose).

Study Objectives: Primary:

Safety:

• To assess the safety and reactogenicity following receipt of two doses of 2017 H7N9 IIV administered intramuscularly at different dosages approximately 21 days apart given with or without AS03 adjuvant

 To assess the serum hemagglutination inhibition (HAI) and neutralizing (Neut) antibody responses following receipt of two doses of 2017 H7N9 IIV administered intramuscularly at different dosages approximately 21 days apart with or without AS03 adjuvant, stratified by age of recipient.

Secondary:

Safety:

- To assess unsolicited non-serious adverse events (AEs) following receipt of two doses of a 2017 H7N9 IIV administered IM at different dosages approximately 21 days apart with or without AS03 adjuvant
- To assess medically-attended adverse events (MAAEs) including new-onset chronic medical conditions (NOCMCs), potentially immune-mediated medical conditions (PIMMCs), and all serious adverse events (SAEs) following receipt of two doses of a 2017 H7N9 IIV administered IM at different dosages approximately 21 days apart with or without AS03 adjuvant

Immunogenicity:

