5.2 Treatment Assignment Procedures

5.2.1 Enrollment and Randomization Procedures

Per ICH guideline E6: Good Clinical Practice (GCP), screening records will be kept at each participating VTEU site to document the reason why an individual was screened, but failed trial entry criteria. The reasons why individuals failed screening will be recorded in the Statistical and Data Coordinating Center's (SDCC) AdvantageEDCSM (Electronic Data Capture System).

Once consented and upon entry of demographic data and confirmation of eligibility for this trial, the subject will be enrolled, randomly assigned to 1 of 5 treatment groups. All subjects will receive 2 vaccinations; the same dose will be given to the subject at both the first and second vaccination. Subjects will be randomized with allocation 2:2:2:1:1 into 5 groups, stratified by site and age (see Table 1) to receive IM 2017 H7N9 IIV at 3.75 mcg, 7.5 mcg or 15 mcg at Days 1 and 22 with AS03 adjuvant or 15 mcg or 45 mcg at Days 1 and 22 administered without adjuvant.

Enrollment of subjects will be done online using the enrollment module of AdvantageEDCSM. The randomization code will be prepared by statisticians at the SDCC and included in the enrollment module for this trial. AdvantageEDCSM will assign each subject to a treatment arm after the demographic and eligibility data have been entered into the system. A designated individual at each participating VTEU site will be provided with a code list for emergency unblinding purposes, which will be kept in a secure place.

Instructions for use of the enrollment module are included in the AdvantageEDCSM User's Guide. Manual back-up procedures and instructions are provided for use in the event that a participating VTEU site temporarily loses access to the Internet or the online enrollment system is unavailable.

Over-enrollment is allowed to account for subjects who do not receive the full schedule of study vaccinations, as shown in Table 1.

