4.4.3. Method of Assigning Subjects to Treatment Groups (Randomization)

Enrollment/randomization will be performed through the enrollment module in the electronic data capture system maintained by the Statistical and Data Coordinating Center (SDCC).

Eligible subjects will be stratified by clinical site and age (19-64 years, ≥65 years) then randomly assigned with allocation (2:2:2:1:1) to one of 5 treatment arms indicated in Table 1. The treatment sequence was generated using permuted block randomization to provide an approximately balanced allocation to the treatment arms during the study.

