8.1. Primary Immunogenicity Analysis

The primary immunogenicity endpoints HAI and Neut seroconversion, percentage of subjects with titer ≥1:40, and GMTs against the homologous A/H7N9 vaccine strain 21 days after the second vaccination will be summarized as described above. Regression modelling of seroconversion and log titers is planned as described in Section 8.3.2.

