8.3.2. Regression Modeling

Logistic and multivariate linear regression will be utilized to test for the effects of the HA antigen dose and the AS03 adjuvant on seroconversion and GMT, respectively, for the PP population. Similar models will be fit for HAI and Neut Antibodies. Separate models will be fit for data from Day 21 post dose 2 and Day 180 post dose 2.

Logistic regression will be fit to examine the relationship of HAI seroconversion at 21 days after the 2nd study vaccination with treatment group and age strata (19-64 years, ≥65 years). If the available titer data meets the required assumptions of normality after log transformation, multiple linear regression will be fit to examine the relationship of log transformed titers at 21 days after the 2nd study vaccination with treatment arm and age strata (19-64 years, ≥65 years). Both models will be fit with and without adjustment for the following covariates (*Z*): sex (female, male), BMI (<30, ≥30), and prior receipt of seasonal influenza vaccine (none in past 2 seasons, at least once in past 2 seasons). Modeling assumptions will be checked using standard diagnostic methods (e.g., using the INFLUENCE option in PROC LOGISTIC or PROC GLM). Parameter estimates and odds ratio estimates for the logistic models will be presented in Table 53, Table 54, Table 55, Table 56, Table 57, Table 58, Table 59, and Table 60. Parameter estimates for the multiple linear regression models will be presented in Table 61, Table 62, Table 63, Table 64, Table 65, Table 66, Table 67, and Table 68.

Model 1A: Logistic Regression (without covariate adjustment):

 $logit[P(seroconversion)] = \beta_0 + \beta_1 \times Treatment + \beta_2 (Age \ge 65) + \varepsilon$

Model 1B: Logistic Regression (with covariate adjustment):

$$logit[P(seroconversion)] = \beta_0 + \beta_1 \times Treatment + \beta_2 (Age \ge 65) + \beta_3 \times Z + \varepsilon$$

Model 2A: Multiple Linear Regression (without covariate adjustment):

$$log(titer) = \beta_0 + \beta_1 \times Treatment + \beta_2(Age \ge 65) + \varepsilon$$

Model 2B: Multiple Linear Regression (with covariate adjustment):

$$log(titer) = \beta_0 + \beta_1 \times Treatment + \beta_2(Age \ge 65) + \beta_3 \times Z + \varepsilon$$

Subjects missing data for one or more covariates will be excluded from Models 1B and 2B.

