9.3.1. Solicited Events and Symptoms

Systemic solicited adverse events were collected pre-vaccination, and systemic and local solicited adverse events were collected at-least 20 minutes post-vaccination and then daily for 7 days after each vaccination and graded on a scale of 0 (absent), 1 (mild), 2 (moderate) and 3 (severe). Systemic events include fever, feverishness, fatigue, malaise, myalgia, arthralgia, headache, and nausea. The grading scale for systemic events, including quantitative grading for fever, is included in Table 11. Local events include pruritus, ecchymosis, erythema, induration/swelling, pain, and tenderness. Ecchymosis, erythema, and induration are measured by both functional and measurement grading scales as defined in Table 10.

When calculating the incidence of solicited events, each subject will be counted once at the highest severity following the applicable vaccination, and any repetitions will be ignored. For summaries presented separately for each vaccination, the denominator for percentages will be the number of subjects who received the respective vaccination with non-missing data for the event summarized. For summaries over all vaccinations the denominator will be the number of subjects who received at least one vaccination with non-missing data for the event summarized.

The number and percentage of subjects reporting at least one solicited adverse event of any severity will be summarized for each solicited symptom, any systemic symptom, any local symptom, and any symptoms. For each event the denominator is the number of subjects who received the applicable vaccination with non-missing data for the specific event. The 95% CI calculated using Clopper-Pearson methodology from a binomial distribution (SAS Proc Freq with a binomial option) will be presented (Table 75, Table 76, Table 77, Table 78, Table 79, and Table 80). Logistic regression models will be fit to estimate the effect of treatment and age on the probability of reporting any local event or reporting any systemic event (Table 81 and Table 82). If statistically significant effects are observed in the model for local events or systemic events, then additional models will be fit for each individual event of that type.

$$logit[P(Event)] = \beta_0 + \beta_1 \times Treatment + \beta_2 (Age \ge 65) + \varepsilon,$$

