Model Parameter	Parameter Levels	Parameter Estimate	SE	95%CI	p-value
Intercept		xxx.x	xxx.x	-	x.xxx
Treatment	3.75 mcg with AS03 adjuvant (reference)	-	-	-	-
	7.5 mcg with AS03 adjuvant	xxx.x	xxx.x	xx.x-xx.x	x.xxx
	15 mcg with AS03 adjuvant	xxx.x	xxx.x	xx.x-xx.x	x.xxx
	15 mcg without AS03 adjuvant	xxx.x	xxx.x	xx.x-xx.x	x.xxx
	45 mcg without AS03 adjuvant	xxx.x	xxx.x	xx.x-xx.x	x.xxx
Age	19-64 years (reference)	-	-	-	-
	≥65 years	xxx.x	xxx.x	xx.x-xx.x	x.xxx
Interaction: Age*Treatment	Age*3.75 mcg with AS03 adjuvant	-	-	-	-
	Age*7.5 mcg with AS03 adjuvant	xxx.x	xxx.x	xx.x-xx.x	x.xxx
	Age*15 mcg with AS03 adjuvant	xxx.x	xxx.x	xx.x-xx.x	x.xxx
	Age*15 mcg without AS03 adjuvant	xxx.x	xxx.x	xx.x-xx.x	x.xxx
7777 11 11 11 11 11 11 11 11 11 11 11 11	Age*45 mcg without AS03 adjuvant	xxx.x	xxx.x	xx.x-xx.x	x.xxx

N = XX subjects with results available at 21 days post second vaccination in the per protocol population. XX subjects missing covariate data were excluded from this analysis. P-value for Treatment = 0.XXX; P-value for Age = 0.XXX; P-value for interaction of Treatment and Age = 0.XXX.

- Table 62: Multiple Linear Regression Model to Evaluate the Relationship of HA Antigen Dose and AS03 Adjuvant with Log-Adjusted Neut Titer at 21 Days Post Second Study Vaccination, Per Protocol Population*
- Table 63: Multiple Linear Regression Model to Evaluate the Relationship of HA Antigen Dose and AS03 Adjuvant with Log-Adjusted HAI Titer at 180 Days Post Second Study Vaccination, Per Protocol Population*
- Table 64: Multiple Linear Regression Model to Evaluate the Relationship of HA Antigen Dose and AS03 Adjuvant with Log-Adjusted Neut Titer at 180 Days Post Second Study Vaccination, Per Protocol Population*

Table 65: Multiple Linear Regression Model to Evaluate the Relationship of HA Antigen Dose and AS03 Adjuvant with Log-Adjusted HAI Titer at 21 Days Post Second Study Vaccination, Adjusted for Baseline Covariates, Per Protocol Population*

Model Parameter	Parameter Levels	Parameter Estimate	SE	95%CI	p-value
Intercept	-	XXX.X	xxx.x	-	x.xxx
Treatment	3.75 mcg with AS03 adjuvant (reference)	-	-	-	-
	7.5 mcg with AS03 adjuvant	xxx.x	xxx.x	XX.X-XX.X	x.xxx
	15 mcg with AS03 adjuvant	xxx.x	xxx.x	xx.x-xx.x	x.xxx
	15 mcg without AS03 adjuvant	xxx.x	xxx.x	XX.X-XX.X	x.xxx
	45 mcg without AS03 adjuvant	xxx.x	xxx.x	XX.X-XX.X	x.xxx
Age	19-64 (reference)	-	-	-	-
	≥65	xxx.x	xxx.x	XX.X-XX.X	x.xxx
Interaction: Age*Treatment	Age*3.75 mcg with AS03 adjuvant	-	-	-	-

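### Site is a randomisation stratum but is left out of the linear log-titer models; adding it costs almost nothing and gains a little

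*SAP*

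**What the plan says.** Both documents make site a stratification factor. Protocol 5.2.1 states "Subjects will be randomized with allocation 2:2:2:1:1 into 5 groups, stratified by site and age", and SAP 4.4.3 states "Eligible subjects will be stratified by clinical site and age". The Protocol Summary allows "Up to 9 Vaccine and Treatment Evaluation Unit (VTEU) sites".

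SAP 6.7 then sets site aside: "Although randomization was stratified by site, data will be pooled across all clinical sites for all analyses". Its reasons are that vaccination and adverse-event assessment are standardised and that one central laboratory runs the immunogenicity assays.

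SAP 8.1, the primary immunogenicity section, adds that "Regression modelling of seroconversion and log titers is planned as described in Section 8.3.2". Section 8.3.2 describes Models 1A/1B (logistic) and 2A/2B (linear): "Both models will be fit with and without adjustment for the following covariates", namely sex, BMI and prior seasonal vaccination. Models 3 and 4 replace the age stratum with age in years. All contain treatment and age; none contains site. The equations have no age-by-treatment term, but the table shells print one and carry the footnote "P-value for Treatment = 0.XXX; P-value for Age = 0.XXX; P-value for interaction of Treatment and Age = 0.XXX".

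The solicited-event logistic models in SAP 9.3.1 also use treatment and age only. If effects are significant, "additional models will be fit for each individual event of that type".

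**The concern.** The plan treats its two stratification factors differently: age is in every model and site is in none. Stratifying by site balances the arms within sites. An analysis that ignores site does not credit that balance: between-site variation stays in the residual, and the model-based standard error exceeds the true sampling variability of the contrast.

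The reasons in SAP 6.7 cover procedures and the assay, not who is enrolled. Protocol section 5 wants each site's enrolment to mirror its own local community. Protocol 2.1 lists age, previous influenza infection or vaccination, and underlying disease as influences on response. Protocol 2.2 and 6.2 have vaccine and adjuvant mixed at each site by its own pharmacist. None of this proves a site effect, but SAP 6.7 does not rule one out.

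At stake is a small loss of precision in the regressions, which are the only planned between-arm immunogenicity estimates. Tables 29-36 report each arm separately.

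**Working it through.** **The plan's own figure.** The only stated power figures are in Protocol Table 5 (SAP Table 6), for differences in responder proportions between two adjuvanted arms. Exact enumeration of the two-sided likelihood ratio test at alpha 0.05 reproduces 11 of the 12 cells to two decimals. The exception is 0.1655 against a printed 0.16, at comparator 0.80 with N = 50. These figures concern proportions and do not change with this point. The documents give no SD, effect size or power for log titer.

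**Inputs from the documents.**
- 100 + 60 subjects per adjuvanted arm and 50 + 30 per unadjuvanted arm (Protocol 11.4.3).
- Per-protocol exclusion of 5% (19-64) and 12% (≥65) (Protocol 11.4.2).
- Analysed: 400 × 0.95 + 240 × 0.88 = 380 + 211 = about 591. Per adjuvanted arm: 95 + 53 = 148.
- Up to 9 sites; permuted blocks at 2:2:2:1:1.

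**Assumptions.** Block size 8 (2+2+2+1+1, the smallest possible); 9 unequal sites holding 3-22% of subjects; between-site share of variance 2%, 5% or 10%; a 0.325 SD difference between 15 mcg + AS03 and 3.75 mcg + AS03.

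**Large-sample check.** With site in the model, the SE is multiplied by √(1 − share). Omitting site therefore overstates it by 1/√0.98 = 1.010, 1/√0.95 = 1.026 and 1/√0.90 = 1.054.

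**Power check without site.** Φ(0.325/√(2/n) − 1.96):
- n = 148: Φ(2.80 − 1.96) = 80%
- n = 95: Φ(2.24 − 1.96) = 61%
- n = 53: Φ(1.67 − 1.96) = 39%

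**Simulation, Model 2A** (8,000 trials per cell; Monte Carlo SE of the power difference 0.13-0.28 points). Power is shown without → with site.

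| Assumed site share | SE overstated (as printed) | 19-64 contrast, as printed | ≥65 contrast, as printed | Equation form, no interaction |
|---|---|---|---|---|
| 2% | 0.9% | 59.8 → 60.2% | 37.5 → 38.0% | 77.8 → 78.2% |
| 5% | 2.5% | 60.4 → 61.9% | 37.1 → 38.9% | 78.7 → 79.9% |
| 10% | 5.2% | 60.2 → 64.1% | 36.7 → 40.4% | 79.3 → 82.0% |

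Type I error for the printed 19-64 row, without versus with site, is 5.1 vs 5.2%, 4.2 vs 4.7% and 3.9 vs 4.7% (Monte Carlo SE 0.24). Omission is conservative. Six unequal sites give SE ratios of 1.0095, 1.0248 and 1.0524.

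**Covariate-adjusted models.** SE overstatement at 2%, 5% and 10%:
- Model 2B: 1.0%, 2.6% and 5.4% if the covariates absorb none of the site difference. If they absorb about half, 0.4%, 1.2% and 2.5%, with power gains of 0.2, 0.6 and 2.0 points (19-64).
- Model 4: 0.9%, 2.5% and 5.3%; or 0.4%, 1.1% and 2.4% with half absorbed.

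**Separate simulation of the equation form** (3,000 runs, 0.322 SD, site effects scaled differently). SE factors with site are 0.992, 0.979 and 0.958, equivalent to overstatement of about 0.8%, 2.1% and 4.4%. Power is 79.5 → 80.1%, 78.7 → 80.2% and 80.8 → 83.8%.

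**Cost if site has no effect.** Eight degrees of freedom, leaving 577 instead of 585 in Model 2A, and an SE about 0.1% larger.

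**On the titer scale.** With an assumed SD of 1.2 for ln titer, the 95% CI factor for a GMT ratio (n = 148 per arm) is exp(1.96 × 1.2 × √(2/148)) = 1.314. At a 10% site share, adjusting for site brings it to 1.296.

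**Logistic models.** Site adjustment is less simple here. The odds ratio becomes conditional on site, its SE rises (by about 1% in simulation with no site effect), and a site with all or no responders causes separation. With N = 591, 75% adjuvanted and 9 unequal sites, the chance of at least one such site is about 0% at assumed response rates of 60%/10% (adjuvanted/unadjuvanted), 10% at 17.5%/3% and 75% at 5%/2%.

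**The case against.** The sponsor considered this and gave its reasons. The models sit under exploratory section 8.3, the trial tests no formal hypothesis (SAP 6.8), and the per-arm primary summaries do not change. Power is therefore a weak yardstick.

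The contrast shown is also the favourable one. For the adjuvant comparison in Protocol Tables 6 and 7, even 50% versus 10% responders corresponds to about 1.28 SD under normal log titers with equal SDs. That gives z = 1.28/√(1/95 + 1/47) = 7.2 in the younger stratum and 1.28/√(1/53 + 1/26) = 5.3 in the older. Power exceeds 99.9% with or without site.

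The linear models are also conditional: SAP 8.3.2 fits them only if log titers look normal. Values below 10 are set to 5 and the unadjuvanted arms are expected to respond poorly, so they may not be fitted at all. No document supports a site share as high as 10%, and at 2% the gain is barely visible. Finally, the parallel linear and logistic models would adjust for different factors.

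All of this stands as a limit on size. None of it shows a disadvantage to the linear estimates, since the worst case is an SE about 0.1% larger. The supportive logistic fit largely answers the loss of parallel structure.

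**Conclusion.** The point holds as a minor, near-free improvement. Site is a stratification factor that the linear log-titer models omit. If it affects titer, the planned standard errors are conservative by about 1% to 5% for assumed site shares of 2% to 10%, and by roughly half that if sex, BMI and prior vaccination absorb half the site difference. Power for a modest dose contrast among adjuvanted arms rises by about 0.4 to 4 points without such absorption. The large adjuvant contrast gains essentially nothing. No conclusion is threatened: the contrast is unbiased and the type I error is, if anything, below nominal.

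These sizes rest on the assumed shares, effect, block size and site distribution, and on the linear models being fitted. The logistic models are a different case, in which site adjustment is cheap but not free.

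**What to change.** Amend SAP 6.7 and 8.3.2 before unblinding:

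- Keep the per-arm descriptive tables pooled across sites.
- Include site as a fixed effect in Models 2A, 2B and 4, and add site rows to Tables 61-68 and 70.
- In the logistic models (Tables 53-60, 69, 81, 82 and any individual-event models), fit site only as a supportive analysis. Alternatively, fix a rule in advance for combining sites that uses event counts as well as site size, such as at least 5 responders and 5 non-responders, summed over arms, in each retained category.

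If the sponsor prefers to keep the pooled linear models, the acceptable minimum is to pre-specify the site-adjusted versions of 2A, 2B and 4 as a sensitivity analysis.

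The linear change costs SAP wording, one class variable, and up to 8 estimate rows plus a reference row in nine shells. The logistic option costs more: site-conditional odds ratios and a combining rule. Under the example rule, about 8.9, 7.6 and 3.6 of 9 site categories would remain at response rates of 60%/10%, 17.5%/3% and 5%/2%, so a site term is of little use for rare events.
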